### 9.1.3.3 Extension Phase

The Extension Phase consists of 2 periods:

- **Treatment Continuation Period**, during which subjects will continue in Cycle 2 and beyond to receive the same treatment they received during the Treatment Phase.  
The **Treatment Continuation** period will start at the end of the Treatment Phase and will end with the completion of the Off-Treatment Visit (which will occur within 30 days after the last administration of the study drug). It consists of study drug treatment on a 21-day cycle, regardless of dose interruptions. Subjects will undergo safety and efficacy assessments as defined in Schedule of Procedures ([Section 9.5.6.1](#)) . Subjects will discontinue the study drug and become Off-Treatment at the time of disease progression, development of unacceptable toxicity, withdrawal of consent or termination of the study program.
- A **Follow-Up Period**, for study assessments after discontinuation from study treatment.  
The **Follow-up Period** will begin the day after the Off-Treatment Visit and will continue as long as the study subject is alive until the completion of the primary analysis, unless the subject withdraws consent or until the sponsor terminates the study. Subjects, who discontinue study treatment without disease progression will continue to be followed and undergo tumor assessments every 6 weeks until disease progression or until the start of another anticancer treatment. In the follow-up period, subjects will be treated by the investigator according to the prevailing local standard of care. Subjects will be followed every 12 weeks ( $\pm 1$  week) for survival, performance status and subsequent anticancer treatments. The sponsor may decide to terminate survival follow-up anytime during the Extension Phase or when all subjects have discontinued study treatment.

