##### **Secondary Efficacy endpoints:**

- Objective response rate

The ORR is the proportion of subjects achieving a best overall response of confirmed partial or complete response (irPR + irCR), according to irRECIST ([Appendix 1](#)) from first dose date until disease progression/recurrence. Subjects who do not have a tumor response assessment for any reason will be considered nonresponders and will be included in the denominator when calculating the response rate.

- Duration of response

Duration of response is defined as the time from the date of first documented confirmed irCR/irPR until the first documentation of confirmed disease progression or death, whichever comes first.

- Progression-free survival

Progressive-free survival is defined as the time from first dose date to the date of the first documentation of confirmed disease progression or death (whichever occurs first) using irRECIST. The censoring rule for events will be defined in the SAP.

- Disease control rate

The DCR is the proportion of subjects achieving irPR + irCR + irSD from first dose date until disease progression/recurrence.

- Clinical benefit rate

The CBR is the proportion of subjects achieving irPR + irCR + irSD [lasting at least 24 weeks] from first dose date until disease progression/recurrence.

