### 9.7.1.7 Efficacy Analyses

The ORR, response duration, time to response, PFS, DCR, and CBR will be listed and descriptively summarized as appropriate.

- Response duration and time to response: Summary statistics (median Q1, Q3, and range) for will be summarized on subjects achieving a best overall response of confirmed partial or complete response (irPR + irCR). The time to response will be censored at the last tumor assessment for subjects who leave the study before a response, death or progression is observed.
- PFS: Subjects who discontinue from the study for reasons other than progression of disease will be treated as right-censored observations at the time of the last response evaluation (subjects who withdraw from the study due to progressive disease will be considered to have a disease progression between the last visit and the time of withdrawal). PFS (by irRECIST) will be reported in both summary tables and Kaplan–Meier curve.

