### 9.7.2 Determination of Sample Size

The sample size of 30 to 40 subjects is considered adequate for the purposes of selecting a dose.

The expected sample size for the dose escalation part of this trial will be up to 24 subjects. Per the dose escalation design adopted and modified from the traditional 3+3 design ([Section 9.1.1.1](#)), there will be a maximum of 4 planned cohorts and there will be 6 subjects each cohort to allow for adequate assessment of tolerability, clinical benefit, PK, PD data and integrated evaluation of safety so as to select RP2D. Additional 6 to 16 subjects will be enrolled in the expansion cohort to confirm RP2D.

The dose escalation part and the extension part yield a total maximum sample size of 40 subjects.

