The time to response (TTR) is defined as the elapsed time (weeks) from the first dose date to the documented start date of confirmed irCR/irPR according to irRECIST. The descriptive statistics for the TTR will be summarized by dose group for the patients with the BOR of confirmed irCR/irPR.

Duration of Response (DOR)

The duration of response (DOR) is defined as the time (months) from the documented start date of confirmed irCR/irPR according to irRECIST until the documented start date of irPD or death (whichever occurs first).

For subjects with the BOR of irCR/irPR who did not die and had no documented progression before the cut-off date for the end of the study, or before early discontinuation (including discontinuations due to toxicity, undocumented clinical progression, change of cancer treatment, or decreasing performance status), and who died or progressed after more than one missed visit, will be censored on the date of their last assessment with the BOR of irCR, irPR or irSD.

The descriptive statistics (median and its standard error, Q1 and Q3) for the DOR will be summarized by dose group for the patients with the BOR of confirmed irCR/irPR using Kaplan-Meier method.

Progression-Free Survival (PFS)

Progression-free survival is defined as alive without confirmed irPD using irRECIST at the end of study or certain evaluation time points such as 3 months, 6 months, etc. The time for PFS is defined as the elapsed time from first dose date to the documented start date of irPD or death (whichever occurs first).

In analysis of PFS, the censoring rule is as follows:

- Subjects who did not die and had no documented progression (confirmed irPD) before the cut-off date for the end of the study, or before early discontinuation (including discontinuations due to toxicity, undocumented clinical progression, change of cancer treatment, or decreasing performance status), PFS will be censored on the date of their last evaluable assessment.
- Subjects who died or progressed after more than one missed visit, or non-evaluable assessment, or a combination of two, PFS will be censored on the date of their last evaluable assessment before the death or progression.

The rate for PFS will be summarized by evaluation time point and dose group. The time curve and median of PFS will be estimated and reported by the Kaplan-Meier method.

Disease Control Rate (DCR)

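### Read literally, the SAP's PFS censoring rule drops deaths and confirmed progressions that follow early discontinuation, although the endpoint counts them and the protocol keeps collecting them

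*SAP*

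**What the plan says.** **Endpoint.** Protocol 9.7.1.1 defines PFS as the "time from first dose date to the date of the first documentation of confirmed disease progression or death (whichever occurs first) using irRECIST". SAP 5.4.1 agrees: "The time for PFS is defined as the elapsed time from first dose date to the documented start date of irPD or death". Neither limits the endpoint to time on drug or on study.

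**PFS censoring, bullet 1 (SAP 5.4.1).** For subjects without death or confirmed irPD before the cutoff, "or before early discontinuation (including discontinuations due to toxicity, undocumented clinical progression, change of cancer treatment, or decreasing performance status), PFS will be censored" at the last evaluable assessment. The bullet does not say whether treatment or study is discontinued.

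**PFS censoring, bullet 2.** This begins "Subjects who died or progressed after more than one missed visit", extends the condition to non-evaluable assessments, and censors at the last evaluable assessment before the event.

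**DOR (SAP 5.4.1).** One sentence runs together the cutoff, the same list of discontinuation reasons and, joined by the word and, the missed-visit condition. It does not mention non-evaluable assessments.

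**Follow-up.** Under Protocol 9.1.3.3, subjects who stop treatment without progression "undergo tumor assessments every 6 weeks until disease progression or until the start of another anticancer treatment". Protocol 9.5.2 continues 6-weekly scans for subjects who go off study without progression. Table 6 footnote b follows such subjects to progression or death, and footnote w follows survival.

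**Protocol analysis text.** Section 9.7.1.7 right-censors subjects who leave the study for reasons other than progression, and treats withdrawal for progression as an event. Section 9.7.1.1 leaves the censoring rule to the SAP. Under 9.7.1.7 the efficacy endpoints "will be listed and descriptively summarized as appropriate".

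**The concern.** A censoring rule should say what happens when the endpoint was not observed. Bullet 1, taken at its word, also censors subjects whose endpoint was observed, provided it came after discontinuation. The trial collects those events by design.

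The reasons listed in bullet 1 include falling performance status and undocumented clinical progression. Subjects who stop for these reasons plausibly face a higher risk of progressing or dying next. If so, the censoring is informative and PFS reads too favourably. If not, recorded events are still thrown away.

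The wording also leaves the result to the programmer, because the two bullets can be applied so that the same subject is an event or is censored. PFS is tabulated by dose group, and clinical activity is one input to the RP2D choice (Protocol 9.1.1.4).

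**Working it through.** The documents give no PFS rate, event target or error rate to reproduce. The only related figure is the sample size, which is said to "yield a total maximum sample size of 40 subjects". That closes: 4 × 6 + 16 = 40.

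**Step 1. Apply the rules to two timelines.** In both, the Day 42 scan shows irSD and the subject discontinues on Day 50 for toxicity.

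| Rule | Scan Day 84 irPD, confirmed Day 126 | Death Day 60 |
|---|---|---|
| Definition | Event, Day 84 | Event, Day 60 |
| Bullet 2 | No missed visit, so not censored | No missed visit, so not censored |
| Bullet 1, literal | Censored | Censored, Day 42 |

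For the irPD case the censoring date is also unclear. It is Day 42 if only assessments before stopping count, but Day 84 or Day 126 otherwise, because bullet 1 does not bound its last assessment by the stop date.

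**Step 2. Treatment or study?** If treatment is meant, Protocol 9.1.3.3 supplies the later scans. If study is meant, Protocol 9.5.2 and Table 6 footnotes b and w still supply scans and deaths. The conflict survives both readings. The exception is a change of cancer treatment: scanning ends there, and only deaths are collected afterwards.

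**Step 3. DOR.** Read strictly, the conjunction means that only late events (after more than one missed visit) are censored, and a responder who is event-free at cutoff has no rule. Read as a list of three separate cases, the sentence works but repeats the PFS problem.

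**Step 4. Illustrative size.** Apart from the 6-weekly scans, every assumption here comes from outside the documents.

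*Model A.* 40,000 simulated subjects per scenario; exponential PFS with median 8, 12 or 18 weeks; 10%, 20% or 40% stopping early by 24 weeks; hazard after stopping unchanged or tripled; 20% of events are deaths; 52-week cutoff. Kaplan-Meier PFS at 26 weeks, post-stop events counted versus bullet 1 taken literally:

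- Hazard unchanged: the difference is 0.6 points or less in every scenario (largest 24.5% versus 23.9%).
- Hazard tripled: bullet 1 overstates PFS by 0.9 points (10.9% versus 11.8%; median 8 weeks, 10% stopping) up to 8.3 points (29.8% versus 38.1%; median 18 weeks, 40% stopping). The middle case (median 12 weeks, 20% stopping) is 21.1% versus 24.2%, or 3.1 points.
- Either way, about 1.5 to 10 events per 40 subjects fall within 12 weeks of stopping and are lost.

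*Model B.* A share q of subjects stop within 4 weeks before their event, so informative stopping is built in; 30% of events are deaths. Week 18 PFS, true versus bullet 1, at median 12 weeks:

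- q = 10%: 35.5% versus 38.8%, +3.3 points
- q = 20%: 35.3% versus 42.1%, +6.8 points
- q = 30%: 35.7% versus 46.4%, +10.7 points

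**Step 5. Against sampling error.** With SE = √(p(1 − p)/n) and p = 0.35:

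- n = 6: √(0.2275/6) = 0.195, about 19 points; a 6.8-point shift is about 0.35 SE
- n = 22 (6 + 16 at the RP2D): √(0.2275/22) = 0.102; about 0.67 SE
- n = 40: √(0.2275/40) = 0.075; about 0.9 SE

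**The case against.** **The protocol censors too.** Section 9.7.1.7 right-censors study discontinuation for non-progression reasons, and bullet 1 largely elaborates that. This stands in part. A reader might infer that the SAP simply departs from the protocol, but the documents do not support that: the conflict is partly inherited. It still has to be settled in the SAP, because Protocol 9.7.1.1 assigns the rule there.

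**Discontinuation may mean leaving the study.** Protocol 9.5.9 lists adverse events among the reasons for discontinuing the study, so this is a live reading. It would be too strong to state as fact that bullet 1 means stopping drug. Step 2 shows that the defect does not depend on it.

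**The bullets may be cumulative.** That bullet 2 preserves other events is an inference from its silence, and either bullet could be meant to censor on its own. It is also possible to attach the discontinuation phrase to progression only, so that deaths still count. These readings are available, but under both a confirmed irPD found after stopping is lost against the definition.

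**DOR is not the same defect.** Correct. A reader might infer that DOR repeats the PFS rule, but its conjunction makes it a garbled sentence that needs its own rewrite.

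**The bias is assumed.** Also correct. With unchanged hazard it is negligible. A reader might also infer a longer median PFS. Model B gives 12 versus 18 weeks when the true median is 12, but only because that median sits on a scan date. At true medians of 8, 10 or 14 weeks the Kaplan-Meier median does not move, and in Model A it is essentially unchanged. No median shift should be claimed.

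**Conclusion.** The point holds as a drafting defect with analytic consequences. Bullet 1, read literally, discards deaths and confirmed irPD that the endpoint definition counts and that the protocol collects, under either meaning of discontinuation. Two programmers could produce different PFS curves from the same data.

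The size cannot be derived from the documents. It ranges from negligible, with non-informative stopping, to roughly 1 to 8 points at 26 weeks if the hazard triples, and 3 to 11 points at Week 18 if stopping closely precedes the event. In a six-subject dose group this is small against the standard error. No test, sample size or error rate depends on PFS or DOR. The change should be made because it is cheap and restores recorded events, not because it would be expected to alter a formal conclusion.

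**What to change.** In SAP 5.4.1, delete the early-discontinuation clause with its list of reasons from the PFS and DOR text, and state:

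> Confirmed irPD or death is an event whether or not study drug or study participation has been discontinued, unless it comes after more than one missed or non-evaluable assessment or after new anticancer therapy has started. Such events are censored at the last evaluable assessment before the gap or before the new therapy, the earlier if both apply. Subjects with no confirmed irPD or death by the data cutoff are censored at the last evaluable assessment before the cutoff, or before new anticancer therapy if that started first.

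Censoring at new therapy keeps the one listed reason that matches where protocol scanning ends, and the text gives a date in every case. Apply the same rule, including non-evaluable assessments, to DOR and to the modified RECIST 1.1 analyses in SAP 5.4.2, with unconfirmed PD as the event there. Align the PFS sentence in Protocol 9.7.1.7.

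The cost is SAP wording, programming and the reconciliation of one protocol sentence. No new data are needed. PFS and DOR may read slightly less favourably.

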**Table 3 Imaging and Treatment After 1st Radiologic Evidence of PD**

	Clinically Stable		Clinically Unstable	
	Imaging	Treatment	Imaging	Treatment
1st radiologic evidence of PD	Repeat imaging at $\geq 4$ weeks at site to confirm PD	May continue study treatment at the investigator's discretion while awaiting confirmatory scan by site	Repeat imaging at $\geq 4$ weeks to confirm PD per physician discretion only	Discontinue treatment
Subsequent scan confirms PD	No additional imaging required	Discontinue treatment	No additional imaging required	N/A
Subsequent scan shows SD, PR, or CR	Continue regularly scheduled imaging assessments	Continue study treatment at the investigator's discretion	Continue regularly scheduled imaging assessments	May restart study treatment if condition has improved and/or is clinically stable per investigator's discretion

CR = complete response, N/A = not applicable, PD = progressive disease, PR = partial response.

Subjects going off study without disease progression will also undergo tumor assessments every 6 weeks until disease progression is documented or another anticancer therapy is initiated.

irRECIST guidelines are described in [Appendix 1](#).

Tumor assessments per modified RECIST 1.1 will follow Eisenhauer et al. (2009), however, up to 10 target lesions, up to 5 per organ, may be selected (as opposed to a maximum of 5 target lesions, up to 2 per organ).

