7 CHANGES IN THE PLANNED ANALYSES

This SAP is in accordance with Clinical Study Protocol v1.0, dated 07 May 2015. No changes to the planned analysis will be applied in this SAP.

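### Protocol 9.7.1.7 counts withdrawal due to progressive disease as a PFS event; SAP 5.4.1 censors the same living subject when the progression is clinical and unconfirmed, and SAP 7 declares no change

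*SAP*

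**What the plan says.** Protocol 9.7.1.7 (Efficacy Analyses) right-censors subjects who discontinue for reasons other than progression, at the last response evaluation. It then sets a separate rule in parentheses: "subjects who withdraw from the study due to progressive disease will be considered to have a disease progression between the last visit". The other end of that interval is the withdrawal itself.

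Protocol 9.7.1.1 (Study Endpoints) defines PFS as running to the "first documentation of confirmed disease progression or death (whichever occurs first) using irRECIST". It adds: "The censoring rule for events will be defined in the SAP".

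SAP 5.4.1 supplies two censoring bullets. The first covers "Subjects who did not die and had no documented progression (confirmed irPD) before the cut-off date for the end of the study"; it applies equally when such a subject discontinues early. The discontinuation reasons it names begin with toxicity and continue: "undocumented clinical progression, change of cancer treatment, or decreasing performance status), PFS will be censored on the date of their last evaluable assessment". The second reads: "Subjects who died or progressed after more than one missed visit, or non-evaluable assessment, or a combination of two, PFS will be censored", at the last evaluable assessment before the death or progression.

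SAP 7 states: "No changes to the planned analysis will be applied in this SAP". It names Protocol v1.0 as the version followed, whereas SAP 3 names Amendment 01.

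**The concern.** Dating an event between last visit and withdrawal is needed only when no visit documented the progression. The protocol's parenthesis therefore addresses the kind of subject whom the SAP censors by name.

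Kaplan-Meier assumes that a censored subject has the same outlook as those still at risk. A subject who leaves because the disease is clinically progressing does not. The gap may also never be closed. Continued six-weekly scans are provided for subjects who stop without progression (Protocol 9.1.3.3 and 9.5.2), so a subject withdrawn for clinical progression may never have the scans needed to confirm irPD. A later death is itself censored if it follows more than one missed visit.

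At stake is how the PFS rates by evaluation time point and dose group are read as evidence of activity, in cohorts of 6 and an expansion of 6 to 16, where one subject is visible.

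**Working it through.** The documents give no PFS rate, median or event count, so there is no stated figure to reproduce. The check has three parts.

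**1. The rules side by side, for a living subject without confirmed irPD**

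| Reason for leaving | Protocol 9.7.1.7 | SAP 5.4.1 |
|---|---|---|
| Progressive disease, clinical only | Event, between last visit and withdrawal | Censored at last evaluable assessment |
| Falling performance status, attributed to progression | Event | Censored |
| Falling performance status, not attributed to progression | Censored | Censored |
| Toxicity | Censored | Censored |

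The documents disagree in the first two rows only.

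**2. Direction of the effect**

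Take one such subject, last scanned at time s and withdrawn at time w. Let n be the number at risk just after s and m the number at risk just before w, both including this subject, with nobody else censored in between. Compare the factor by which each estimate changes after s.

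- Just before w: protocol m/n; SAP (m-1)/(n-1). Since m is at most n, the SAP value is equal or lower.
- From w onward: protocol (m-1)/n; SAP (m-1)/(n-1). The SAP value is higher by the factor n/(n-1), or equal if both are zero. Later risk sets are identical, so the factor persists.

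Example of both effects: 6 subjects, progressions at weeks 6 and 12, a third subject last scanned at week 6 who misses week 12 and withdraws for progression at week 14, and three who stay progression-free.

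- Week 13: protocol (5/6)(4/5) = 0.667; SAP (5/6)(3/4) = 0.625.
- Week 14 onward: protocol 0.667 × 3/4 = 0.500; SAP 0.625.

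**3. Illustration of size**

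From the documents: scans every 6 weeks (Protocol 9.5.2), cohorts of 6, and an expansion of up to 16. Assumed: progressions spread evenly over the intervals ending at weeks 6, 12, 18 and 24; 4 of 16 or 2 of 6 progression-free after week 24; one progression is an undocumented clinical withdrawal, occurring after the first post-baseline scan; no deaths. The withdrawal is censored at the preceding scan, after the events at that scan.

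n = 16, three progressions per interval. Protocol rule: 4/16 = 0.250.

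- Withdrawal in interval 2: (13/16)(10/12)(7/10)(4/7) = 0.271
- Withdrawal in interval 4: (13/16)(10/13)(7/10)(4/6) = 0.292

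n = 6, one progression per interval. Protocol rule: 2/6 = 0.333.

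- Withdrawal in interval 2: (5/6)(3/4)(2/3) = 0.417
- Withdrawal in interval 4: (5/6)(4/5)(3/4) = 0.500

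The factor n/(n-1) gives the same results: 0.250 × 13/12 and 0.250 × 7/6; 0.333 × 5/4 and 0.333 × 3/2. With no such withdrawals the rules agree.

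**The case against.** The strongest reply is that the SAP does what the protocol asks. Protocol 9.7.1.1 makes confirmed irRECIST progression or death the event, and undocumented clinical progression is neither. The same section hands the censoring rule to the SAP. On that view the outlier is a parenthesis in 9.7.1.7. This stands in part: the SAP cannot fairly be called an unauthorised change, and the protocol needs reconciling with itself. But 9.7.1.7 sets a specific rule for this case, and the SAP neither follows it nor records a departure.

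SAP 7 is weaker evidence than it looks. Its no-change statement refers to Protocol v1.0, which was not supplied, so it cannot be checked against that text. The conflict with the protocol in hand remains.

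The affected group may also be small. The parenthesis concerns withdrawal from the study, and subjects who only stop treatment without progression stay on scheduled scans. That limits the likely size, not the inconsistency.

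A reader might infer that clinically unstable subjects with one irPD scan, whose repeat imaging is "to confirm PD per physician discretion only" (Protocol Table 3), are a further departure. Lack of confirmation alone is not: there the SAP follows the protocol's own requirement for confirmed progression. The conflict arises only if such a subject withdraws from the study because of progression.

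PFS by modified RECIST 1.1 (SAP 5.4.2) does not require confirmation of PD, but it does not fill the gap. It is exploratory and is analysed in the same way, so clinical progression without a PD scan is still censored.

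**Conclusion.** The conflict is real and should be resolved before database lock. It is confined to living subjects who withdraw because of progression without confirmed irPD. For them the SAP rule raises the Kaplan-Meier PFS estimate, or leaves it equal, from the withdrawal date onward. The amount depends on how many there are and when they leave, which the documents do not say.

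Three stronger readings are not supported:

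- That every discontinuation for falling performance status is mishandled. Where the decline is not attributed to progression, both documents censor.
- That PFS at 3 or 6 months can only read higher. A time point between the last scan and withdrawal can read lower, as 0.625 against 0.667 at week 13 shows.
- That the illustrated figures are upper limits. They rest on one withdrawal, even spacing and the assumed progression-free counts. In the same 16-subject layout, two withdrawals give from (13/16)(4/11) = 0.295 to (7/16)(4/5) = 0.350.

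PFS is a secondary, descriptive endpoint. No hypothesis test is affected.

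**What to change.** Reconcile SAP 5.4.1 with Protocol 9.7.1.7 by one of two routes, not both:

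1. Count withdrawal due to progressive disease as a PFS event in the main irRECIST analysis, on a stated date inside the 9.7.1.7 interval (for example the withdrawal date); or
2. Keep confirmed irPD or death as the main definition, declare the departure in SAP 7, and add one prespecified irRECIST PFS sensitivity analysis that applies the 9.7.1.7 rule.

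Under either route:

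- Name the CRF field that identifies these subjects, because the study-discontinuation reasons in Protocol 9.5.9 do not list progression.
- Report the number censored for each reason, by dose group.
- Make SAP 3 and SAP 7 cite the same protocol version.

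The cost is SAP wording, one count table and, under the second route, one extra analysis. A CRF change is needed only if withdrawal for progression is not already recorded. The downside is that PFS may look slightly less favourable.
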